4.2 Dose Limiting Toxicity (Tebotelimab Cohort)

For the purposes of safety management and defining DLTs, the combination of enoblituzumab + tebotelimab will be treated as one entity. If a DLT is considered related to study treatment, no distinction will be made as to which agent is the causative agent and administration of both agents will be stopped.

Dose limiting toxicities will be based on treatment-emergent drug-related AEs (or laboratory abnormalities) occurring through Cycle 2 Day 7.

Patients in the Tebotelimab Cohort who experience DLT will discontinue study treatment.

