4.2.3 Hepatic Non-hematologic Dose Limiting Toxicity

Hepatic non-hematologic DLT will be defined as follows:

- Any elevation of one or more transaminases $> 8 \times$ the institutional upper limit of normal (ULN) irrespective of duration.
- Any Grade 3 elevation of one or more transaminases $> 5.0 - 8.0 \times$ the ULN that does not resolve to Grade 2 within 7 days, and Grade 1 or baseline within 14 days. If steroids are administered, they must be tapered to ≤ 10 mg of prednisone or equivalent per day by Day 14. Please see [Section 7.2.2](#) for further management guidelines.
 - For patients with Grade 1 or 2 elevations of transaminases at baseline, a doubling of transaminases will be considered dose limiting, if not resolved to baseline within 14 days.
- Any Grade 3 elevation of total bilirubin that is $> 5 \times$ the ULN irrespective of duration.
- Any elevation of total bilirubin $> 3.0 - 5.0 \times$ ULN that does not resolve to Grade 2 within 7 days and Grade 1 or baseline within 14 days. If steroids are administered, they must be tapered to ≤ 10 mg of prednisone or equivalent per day by Day 14. Please see [Section 7.2.2](#) for further management guidelines.
- Any event meeting the criteria for Hy's law as follows (all three features):
 - Aspartate aminotransferase (AST) and/or alanine aminotransferase (ALT) $> 3 \times$ ULN, or doubling of AST and/or ALT for patient having Grade 2 transaminase levels at baseline.
 - Concurrent elevation of total bilirubin $> 2 \times$ ULN without initial evidence of cholestasis
 - No alternative etiology can be identified.

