4.3.1 Dose Delays

Tebotelimab Cohort

Patients who experience a Grade 2 to 4 AE that is potentially dose-limiting should have study drug held pending assessment, management, and resolution of the AE. If the AE is assessed as unrelated to study drug or does not meet DLT criteria, therapy may be restarted at the previous dose and schedule, after appropriate recovery.

Retifanlimab and Tebotelimab Cohorts

A dose delay of up to 20 days is allowed for patients experiencing AEs. In the case of abnormal troponins or N-terminal pro b-type natriuretic peptide (NT-proBNP) values, study drug must be withheld and a thorough cardiac assessment performed promptly to diagnose myocarditis or other cardiovascular diseases; the patient may resume study drugs if myocarditis is not confirmed. Refer to [Section 7](#) for specific guidance on restarting study therapy for IRR and irAEs. A dose delay of up to 20 days may also be permitted for reasons other than AEs. All procedures at the missed dosing visit should be performed and treatment reinstated as if the delay had not occurred.

Patients with infusion delays > 20 days will discontinue the study drug, complete the End of Treatment visit, and then enter the Post-treatment Follow-up Period.

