7.2.2 Hepatic Toxicity

7.2.2.1 Elevations in Transaminases

- Grade 1 elevations - No specific therapy required.
- Grade 2 elevations - For elevations in transaminases 3 to 5 × ULN, rule out viral and other etiologies. Consider imaging studies such as ultrasound or CT scan and liver biopsy to ascertain etiology of liver dysfunction. Consider starting oral prednisone 60 mg/day divided twice daily, and hold study treatment.
 - If improvement to ≤ Grade 1 does not occur within 48 hours consider IV steroids such as methylprednisolone at 2 mg/kg/day divided twice daily or oral steroids such as prednisone 60 to 120 mg per day, divided twice daily.
 - Monitor liver function tests at least twice weekly (or more frequently as clinically appropriate in the judgment of the Investigator) until transaminases have returned to Grade 1 or baseline.
 - Taper oral steroids as clinically indicated with improvement in liver function.
 - Resume study treatment at the next scheduled dose if no more than two doses were missed.
 - If improvement to ≤ Grade 1 does not occur within 14 days, discontinue study treatment.
- Grade 3 elevations - Hold study treatment.
 - For elevations in transaminases > 8 × ULN, permanently discontinue study treatment.
 - Begin immediate IV steroids; suggest methylprednisolone at a dosage of 2 mg/kg/day divided twice daily.
 - Consider additional immune suppression with mycophenolate for patients who do not respond to corticosteroid therapy within 3 to 5 days.
 - Monitor liver function tests at least twice weekly (or more frequently as clinically appropriate in the judgment of the Investigator) until transaminases have returned to Grade 1 or baseline.
 - For elevations in transaminases > 5 but ≤ 8 × ULN:
 - Begin immediate IV steroids; suggest methylprednisolone at a dosage of 2 mg/kg/day divided twice daily.
 - Consider additional immune suppression as above for patients who do not respond to corticosteroid therapy within 3 to 5 days.

- Monitor liver function tests at least twice weekly (or more frequently as clinically appropriate in the judgment of the Investigator) until transaminases have returned to Grade 1 or baseline.
- If the elevation does not improve to Grade 2 within 7 days and to Grade 1 within 14 days, discontinue study treatment.
- Resume study treatment administration if following conditions are met:
 - Laboratory elevations improved to \leq Grade 2 within 7 days and improve to \leq Grade 1 or baseline within 14 days.

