7.2.2.2 Elevations in Total Bilirubin

- Grade 1 elevations - No specific therapy required.
- Grade 2 elevations - Hold study treatment until improvement to \leq Grade 1.
 - Rule out viral and other etiologies. Consider imaging studies such as ultrasound or CT scan and liver biopsy to ascertain etiology of liver dysfunction. Consider oral steroids.
 - If improvement to \leq Grade 1 does not occur within 14 days, discontinue study treatment and begin oral steroids.
- Grade 3 elevations - Hold study treatment.
 - For elevations in total bilirubin $> 5 \times$ ULN, permanently discontinue study treatment and initiate IV steroids, suggest methylprednisolone at a dosage of 2 mg/kg/day divided twice daily, and,
 - If no response to corticosteroid therapy within 3 to 5 days is observed, consider adding immune suppression therapy with mycophenolate.
 - Monitor liver function testing at least twice weekly (or more frequently as clinically appropriate in the judgment of the Investigator) until total bilirubin has returned to Grade 1 or baseline.
 - For elevations in total bilirubin > 3.0 but $\leq 5 \times$ ULN:

- Begin immediate IV steroids, suggest methylprednisolone at a dosage of 2 mg/kg/day divided twice daily. Consider additional immune suppression as above for patients who do not respond to corticosteroid therapy within 3 to 5 days.
- Monitor liver function including total bilirubin testing at least twice weekly (or more frequently as clinically appropriate in the judgment of the Investigator) until total bilirubin has returned to Grade 1 or baseline.
- If the elevation does not improve to Grade 2 within 7 days and to Grade 1 within 14 days, discontinue study treatment.
- Resume study treatment administration if:
 - Laboratory elevations downgrade to \leq Grade 2 within 7 days and improve to \leq Grade 1 or baseline within 14 days.
 - Steroids have been tapered to \leq 10 mg per day of prednisone or equivalent
 - On resuming study treatment, AST, ALT, and total bilirubin laboratory test values will be evaluated at least once per week for 3 consecutive weeks.
- Permanently discontinue study treatment in the case of a second increase of total bilirubin to \geq Grade 3.
- Grade 4 elevations - Discontinue study treatment and treat as for Grade 3 elevation.

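### The liver-toxicity guidance (Protocol 7.2.2) has no Hy's law stop, so outside the Tebotelimab DLT window its restart rules allow re-dosing after such an event

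*Protocol*

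**What the plan says.** Protocol Section 4.2.3 lists five main hepatic dose-limiting criteria. The fifth opens "Any event meeting the criteria for Hy's law as follows (all three features" and then requires AST and/or ALT above 3 x ULN (or a doubling from a Grade 2 baseline), concurrent total bilirubin above 2 x ULN without initial cholestasis, and no other identifiable cause. It has no recovery clause: once the three features are present, the event is dose-limiting.

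Section 4.2 limits DLTs to drug-related events through Cycle 2 Day 7 and states the consequence for one cohort: "Patients in the Tebotelimab Cohort who experience DLT will discontinue study treatment". Section 4.3.1 fits with this. In the Tebotelimab Cohort, if an event is unrelated or "does not meet DLT criteria, therapy may be restarted at the previous dose and schedule".

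Section 7.2.2 guides liver toxicity for both cohorts with no cycle limit. It has one subsection for transaminases and another for bilirubin.

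- Grade 2 transaminases: consider steroids and hold, then "Resume study treatment at the next scheduled dose if no more than two doses were missed"; discontinue if not at Grade 1 or lower within 14 days.
- Grade 3 transaminases: above 8 x ULN, "permanently discontinue study treatment"; otherwise "Resume study treatment administration if following conditions are met", the conditions being timely laboratory recovery and a steroid taper.
- Bilirubin: "Grade 2 elevations - Hold study treatment until improvement to" Grade 1 or lower. Above 3 and up to 5 x ULN, "If the elevation does not improve to Grade 2 within 7 days and to Grade 1 within 14 days, discontinue study treatment".

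Neither subsection mentions Hy's law or a combined elevation.

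**The concern.** The hepatic DLT list and the liver management section share thresholds and recovery times, so the second reads as the treatment-wide version of the first. One main criterion was not brought across. The restart rules depend only on whether each laboratory value recovers, while the Hy's law criterion depends on the two values having risen together without another cause. An Investigator who follows the restart bullets as written could re-expose a patient to both study drugs after an event that the protocol itself calls dose-limiting. The issue is patient safety; no endpoint or analysis is affected.

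**Working it through.** No figure in the plan needs reproducing. The check has three steps.

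**1. Section 4.2.3 against Section 7.2.2**

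| Main hepatic criterion in 4.2.3 | Stop in 7.2.2? |
|---|---|
| Transaminases > 8 x ULN | Yes, permanent (7.2.2.1, Grade 3) |
| Transaminases > 5 to 8 x ULN, not recovering on the 7-day/14-day schedule | Yes (7.2.2.1, Grade 3) |
| Bilirubin > 5 x ULN | Yes, permanent (7.2.2.2, Grade 3) |
| Bilirubin > 3 to 5 x ULN, not recovering on the 7-day/14-day schedule | Yes (7.2.2.2, Grade 3) |
| Hy's law | None |

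Four of five are carried over.

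**2. Cases run through the written rules**

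- *ALT 4 x, bilirubin 2.5 x ULN, drug-related, no other cause.* Both values are Grade 2, so drug is held. If both return to Grade 1 or lower within 14 days, 7.2.2.1 says to resume at the next scheduled dose and the 7.2.2.2 hold ends.
- *ALT 6 x, bilirubin 2.5 x ULN.* ALT is in the > 5 to 8 x ULN tier. Treatment may resume if ALT reaches Grade 2 within 7 days and Grade 1 or baseline within 14, steroids are down to 10 mg/day prednisone equivalent or less, and bilirubin clears.
- *A second event like the first case.* The repeat-event stops need Grade 3 or higher on one test, so a repeat at Grade 2 on both is not caught.

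The gap therefore covers transaminases > 3 to 8 x ULN with bilirubin > 2 to 5 x ULN and timely recovery. Higher values or slower recovery already end treatment.

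Other provisions that might close it:

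- The DLT stop (4.2) covers one cohort through Cycle 2 Day 7. With 21-day cycles that is 21 + 7 = 28 days, out of a possible 35 x 21 = 735. The Retifanlimab Cohort never has it.
- Table 5 (12.2.4.1) requires potential Hy's law to be reported within 24 hours but states no dosing action.
- Section 4.4 lists adverse events requiring discontinuation as a reason to stop, without saying which qualify.
- Section 4.3.1 ends treatment for delays over 20 days, which a quickly recovering patient would not reach.
- Section 7.2 lets the Investigator adapt the guidance. That permits a stop but does not require one.

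**3. Expected number of events**

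Section 2.3.3.2 describes 230 patients on retifanlimab monotherapy in a study where potential Hy's law was an AESI. It is not among the AESIs named as seen in more than one participant. Taking that list as complete, the count is 0 or 1.

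- If 1: 1/230 = 0.43%, exact (Clopper-Pearson) 95% upper limit 2.40%. In 50 patients: 50 x 0.0043 = 0.22 events, upper 50 x 0.0240 = 1.20.
- If 0: upper limit 1 - 0.025^(1/230) = 1.59%. In 50 patients: up to 0.8.

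These figures count all potential Hy's law events, including those that existing stops would catch, so the number eligible for re-dosing would be smaller. They assume enoblituzumab adds no hepatic risk. The related AEs listed for the 12 enoblituzumab + retifanlimab patients (2.3.2.2) include none that is hepatic. For tebotelimab, Section 2.3.4.2 gives no Hy's law count but reports hepatic treatment-related SAEs: immune-mediated hepatitis in 2 dose-escalation patients, and hepatitis, immune-mediated hepatitis and increased transaminases (1 each) in the expansion cohorts.

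**The case against.** DLT criteria serve an early safety evaluation, and a protocol need not apply them for the whole of treatment. This one does not do so generally: the hematologic DLTs of 4.2.1 have no stopping rule in Section 7, and the 4.2.3 sub-bullet on doubling from an elevated baseline is not carried over either. All of 7.2 is adaptable guidance, so the four carried-over stops are not strictly binding. A Hy's law event already leads to a hold, a search for other causes, a 14-day limit and sponsor notification within 24 hours. After a Grade 3 restart, liver tests are repeated at least weekly for three weeks. What remains is discretionary re-dosing after quick, full recovery with the sponsor informed.

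Most of this is fair, and it limits the size of the problem. It does not explain why, among the main hepatic criteria, only this one was left out of a section that otherwise mirrors them. Nor does it change the written direction for such an event, which is to resume. Adaptable guidance should still point the safe way.

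A further objection is that patients with hepatic metastases may enter with AST/ALT up to 5 x ULN, so some meet the transaminase feature at baseline. This carries less weight: 4.2.3 has a doubling alternative for a Grade 2 baseline and requires that no other cause be found, and the fix uses those same criteria.

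**Conclusion.** The concern holds. Section 7.2.2 carries over four of the five main hepatic DLT criteria and omits Hy's law. In the Retifanlimab Cohort at any time, and in the Tebotelimab Cohort after Cycle 2 Day 7, no written rule requires stopping after a Hy's law event with transaminases up to 8 x ULN and bilirubin up to 5 x ULN that recovers in time. Inside the Tebotelimab DLT window there is no conflict.

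Re-dosing is permitted, not forced, and few patients would be affected: about 0.2 events in the Retifanlimab Cohort, up to 1.2 at the upper limit, borrowing the monotherapy rate. The documents give no basis for an estimate in the Tebotelimab Cohort. The change should be made because the event is serious and the correction is cheap, not because events are expected to be frequent.

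**What to change.** Add at the head of Section 7.2.2:

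> Any event meeting the Hy's law criteria of Section 4.2.3 requires permanent discontinuation of study treatment, in either cohort and at any cycle. The restart conditions in 7.2.2.1 and 7.2.2.2 do not apply to such an event.

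This costs one sentence of protocol text. AST, ALT and total bilirubin are already in the same chemistry panel (Appendix 2), so no visit or test is added. The downside is that a rare patient who recovers fully loses further treatment, which the protocol already accepts for the same event inside the Tebotelimab DLT window.

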7.2.2.2 Elevations in Total Bilirubin

- Grade 1 elevations - No specific therapy required.
- Grade 2 elevations - Hold study treatment until improvement to \leq Grade 1.
 - Rule out viral and other etiologies. Consider imaging studies such as ultrasound or CT scan and liver biopsy to ascertain etiology of liver dysfunction. Consider oral steroids.
 - If improvement to \leq Grade 1 does not occur within 14 days, discontinue study treatment and begin oral steroids.
- Grade 3 elevations - Hold study treatment.
 - For elevations in total bilirubin $> 5 \times$ ULN, permanently discontinue study treatment and initiate IV steroids, suggest methylprednisolone at a dosage of 2 mg/kg/day divided twice daily, and,
 - If no response to corticosteroid therapy within 3 to 5 days is observed, consider adding immune suppression therapy with mycophenolate.
 - Monitor liver function testing at least twice weekly (or more frequently as clinically appropriate in the judgment of the Investigator) until total bilirubin has returned to Grade 1 or baseline.
 - For elevations in total bilirubin > 3.0 but $\leq 5 \times$ ULN:

- Begin immediate IV steroids, suggest methylprednisolone at a dosage of 2 mg/kg/day divided twice daily. Consider additional immune suppression as above for patients who do not respond to corticosteroid therapy within 3 to 5 days.
- Monitor liver function including total bilirubin testing at least twice weekly (or more frequently as clinically appropriate in the judgment of the Investigator) until total bilirubin has returned to Grade 1 or baseline.
- If the elevation does not improve to Grade 2 within 7 days and to Grade 1 within 14 days, discontinue study treatment.
- Resume study treatment administration if:
 - Laboratory elevations downgrade to \leq Grade 2 within 7 days and improve to \leq Grade 1 or baseline within 14 days.
 - Steroids have been tapered to \leq 10 mg per day of prednisone or equivalent
 - On resuming study treatment, AST, ALT, and total bilirubin laboratory test values will be evaluated at least once per week for 3 consecutive weeks.
- Permanently discontinue study treatment in the case of a second increase of total bilirubin to \geq Grade 3.
- Grade 4 elevations - Discontinue study treatment and treat as for Grade 3 elevation.

7.2.3 Pneumonitis

- Grade 1 pneumonitis - No specific therapy required; close monitoring of lung function and imaging.
- Grade 2 pneumonitis - Hold study treatment.
 - Consider corticosteroids: 1 to 2 mg/kg of oral prednisone or equivalent per day divided twice daily.
 - Taper over 4 weeks as clinically indicated.
 - Resume study treatment administration at next scheduled dose if pneumonitis resolves to \leq Grade 1 within 5 days with or without treatment.
- Grade 3 and 4 pneumonitis - Permanently discontinue study treatment.
 - Hospitalize.
 - Recommend a pulmonary consult/diagnostic evaluation including chest X-ray and CT scan.

- Initiate maximal supportive care including IV corticosteroids, suggest methylprednisolone at 2 to 4 mg/kg/day divided twice daily. Higher doses may be used in consultation with the Sponsor's Medical Monitor.
- If no response to corticosteroid therapy is observed within 3 to 5 days, consider adding immune suppression therapy (i.e., infliximab, etc.).

7.2.4 Dermatologic Toxicity

- Grade 1 or 2 skin reactions
 - Symptomatic treatment with low-dose topical corticosteroids (betamethasone 0.1% or hydrocortisone 1%) or antihistamines (diphenhydramine).
 - Persistent Grade 1 or 2 rash should be managed with higher dose topical corticosteroids and/or oral prednisone (1 to 2 mg/kg/day) if there is not improvement with topical therapies or the rash is associated with other dermal toxicities such as pruritus.
- Grade 3 skin reactions – Hold study treatment.
 - Initiate oral corticosteroids (oral prednisone 1 to 2 mg/kg/day).
 - Study treatment administration may be restarted at the next scheduled dosing if symptoms resolve to \leq Grade 2 within 14 days.
 - Grade 3 skin toxicity that does not resolve to \leq Grade 2 within 14 days of initiation of oral corticosteroids requires permanent discontinuation of study treatment.
- Grade 4 skin reactions - Discontinue study treatment.
 - Initiate oral corticosteroids (oral prednisone 1 to 2 mg/kg/day).
 - Consideration should be given to start IV corticosteroids (methylprednisolone 1-2 mg/kg/day) for Grade 4 dermatologic toxicities with tapering on resolution to $<$ Grade 2 over 30 days.

7.2.5 Nephritis

- Grade 1 nephritis - No specific therapy required; close monitoring of renal function.
- Grade 2 nephritis - Hold study treatment.
 - Consider nephrology consultation and renal biopsy to confirm interstitial nephritis.
 - Begin corticosteroids: 1 to 2 mg/kg of oral prednisone or equivalent per day divided twice daily. Taper over 4 weeks as clinically indicated.
 - Resume study treatment administration at next scheduled dose if:

- Nephritis resolves to \leq Grade 1 within 14 days with or without treatment
- Grade 3 and 4 nephritis - Permanently discontinue study treatment.
 - Consider hospitalization, nephrology consultation, and renal biopsy to confirm interstitial nephritis
 - Begin corticosteroids: 2 to 4 mg/kg of oral or IV methylprednisolone or equivalent per day divided twice daily. Taper over 4 weeks as clinically indicated.

7.2.6 Immune-Mediated Hypophysitis

- Grade 1 hypophysitis - No specific therapy required.
- Grade ≥ 2 hypophysitis - Hold study treatment.
 - Consult endocrinologist.
 - Consider hospitalization.
 - Consider short course of high dose IV corticosteroids: e.g., methylprednisolone 2-4 mg/kg IV (or equivalent) divided twice daily.
 - Initiate hormonal replacement as indicated.
 - Study treatment may be resumed as allowed by protocol when:
 - Endocrinopathy is controlled with appropriate replacement therapy.
 - Corticosteroid dose reduced to ≤ 10 mg prednisone or equivalent per day.
 - Brain MRI recommended.

7.2.7 Thyroid Toxicity

Thyroid disorders may occur at any time during treatment with study drugs. Monitor patients for changes in thyroid function per protocol and as indicated based on clinical evaluation and for clinical signs and symptoms of thyroid disorders. Isolated hypothyroidism may generally be managed with replacement therapy without treatment interruption and without corticosteroids, and a suggested treatment guideline for hyperthyroidism is described below:

- Grade 1 hyperthyroidism - No specific therapy required.
- Grade 2 hyperthyroidism - Hold study treatment.
 - Consider starting oral corticosteroid therapy.
 - Short course of corticosteroid such as methylprednisolone 1 to 2 mg/kg IV (or equivalent) divided twice daily.

- Resume study treatment if corticosteroid dose is reduced to ≤ 10 mg prednisone or equivalent per day and stable on hormone replacement therapy (if necessary).
- Grade 3 or 4 hyperthyroidism - Hold study treatment.
 - Consider hospitalization and consulting endocrinologist.
 - Begin IV corticosteroids such as methylprednisolone 2 to 4 mg/kg IV (or equivalent) divided twice daily.
 - Initiate hormonal replacement as necessary.
 - Consider restarting study treatment with complete resolution, or if stable on hormone replacement therapy within 14 days, and if corticosteroid dose is reduced to ≤ 10 mg prednisone or equivalent per day.

